## 4.0 TREATMENT PLAN

## 4.1 Overview

Patients will be treated with either Tremelimumab 75 mg alone, MEDI4736 750 mg alone, or both in combination. Patients will be randomly allocated using block randomization to ensure equal sample sizes per arm. Up to 45 patients (15 per arm) will be randomized to ensure that 30 patients are evaluable for immunologic response (10 per arm).

Patients will then undergo a surgical resection of their tumor that is part of their medical care 2 weeks later to remove the tumor. Two weeks is expected to be enough time for immunologic changes to occur in the tumor. Standard pre-surgical testing will be done prior to surgery. At the time of surgery, tissue will be removed for local pathology review and send to [name] for evaluation (see Section 9.0 for details).

Post-operative care will be standard for patients who undergo a craniotomy and tumor resection at NMH. Patients will have a standard post-operative MRI or CT scan of the brain within 72 hours of surgery. Following surgery, patients will resume treatment on the same regimen they were assigned to receive before surgery. Treatment may continue until disease progression or unacceptable toxicity.

Treatment Administration Summary					
Arm	Treatment	Dose	Route	Schedule	Supportive Therapies**
1	Tremelimumab monotherapy	75 mg	IV at 250ml/hr	Once within 14 d (+/-3) pre-surgery. Adjuvant: Every 4 weeks	Acetaminophen and/or antihistamine or equivalent 
2	MEDI4736 monotherapy	750 mg	IV over 60min+/-5 mins 	Once within 14 d (+/-3) pre-surgery. Adjuvant: Every 2 weeks	Acetaminophen and/or antihistamine or equivalent 

#### 4.2 Treatment Administration

3	Tremelimumab + MEDI4736 combination therapy	75 mg + 750mg	IV  1 hour for each drug	Once within 14 d (+/-3) pre-surgery. Then, treme every 4 weeks (for 7 doses post- surgery) + MEDI every 2 weeks (for 14 doses post- surgery); then Treme every 12 weeks and MEDI every 2 weeks from C7 (wk 25).	Acetaminophen and/or antihistamine or equivalent 
---	--	------------------	--	---	---

1 Tremelimubab administered first, then MED14736 infused after a gap of 1 hour for the first cycle. If tolerated, then can be given one after the other for subsequent infusions (at discretion of PI)

2 Use a 0.2 micron in-line filter

3 As per institutional policy, at the discretion of the investigator. May also be used as pre-medications for infusions

\*\*Antiemetic therapy may be used as needed; 5HT antagonists are recommended. Hematopoietic growth factors (G-CSF) may be used per ASCO guidelines after cycle one. Corticosteroids should be used in the smallest dose to control symptoms of cerebral edema and mass effect, and should be discontinued if possible. Febrile neutropenia may be managed according to the institution's infectious disease/ASCO guidelines.

Patients will be allocated randomly using block randomization to ensure equal sample sizes per arm, with up to 12 patients being enrolled into each arm (in order to achieve 10 evaluable per arm). On

all arms, patients will be given the 1st dose(s) of study treatment 14 days pre-surgery. Patients will then undergo standard surgical resection. Dosing will then resume approximately 14 days after surgery (once the surgical wound has healed) and will follow the schedule outlined above (depending on the arm to which they were assigned). For the combination Arm 3. Tremelimumab will be administered IV every 4 weeks (Day 1 of each cycle) and MEDI4736 750mg every 2 weeks (Day 1 and Day 15 of each cycle) until the patients have received 7 doses of Tremelimumab and 14 doses of MEDI4736, post-surgery. Thereafter, from Cycle 7 (Week 25), Tremelimumab will be given every 12 weeks (+/-7 days) and MEDI4736 will be given every 2 weeks (+/- 2 days) until permanent discontinuation criteria (e.g. disease progression) is met. On all arms, if there is no progression of disease, patients may continue on treatment for up to 24 months. If at the time of progression, the patient is a candidate for surgery, tissue will again be sent to [name] laboratory for evaluation.

Any patient who has disease progression as defined in section 6.0 or clinical decline and undergoes further surgery will have the option to use their tumor tissue for research to understand the immunologic changes occurring at the time of presumed drug failure. If on pathologic review, there is no evidence of significant tumor and the changes on MRI were likely treatment related, the patient will be allowed re-start treatment. The patient will be advised of the pathology results and that they may not derive any further benefit from therapy and they will need to re-sign the informed consent prior to starting therapy.

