# STUDY SCHEMA

# STUDY SUMMARY

	A Phase II, open label, single center study of pre-surgical and adjuvant treatment of recurrent glioblastoma with Tremelimumab and MEDI4736 alone and in combination to
Title	determine immunologic changes from treatment.
Version	11.29.18
Study Design	Phase II trial
Study Center(s)	Robert H. Lurie Cancer Center of Northwestern University.
Objectives	
 
Primary: 
 
To determine the T-cell changes that occur in recurrent GBM treated with tremelimumab and durvalumab as single agents and in combination.
 
 
 
Secondary: 
 
To evaluate the safety of either tremelimumab or MEDI4736 alone and in combination in patients with recurrent GBM.
 
To determine post-surgery, the time to progression (per Modified RANO criteria and iRANO criteria, see below) for patients treated with either Tremelimumab or MEDI4736 alone and in combination of both.
 
To determine post-surgery, the overall survival for patients treated with Tremelimumab or MEDI4736 alone and in combination of both.
 
To assess post-surgery, the MRI changes in patients treated with either Tremelimumab or MEDI4736 alone and in combination of both.
 
 
 
Exploratory: 
 
To correlate T-cell changes and PDL1 expression with patient outcomes.
 
 
 

Sample Size	There will be three groups of patients, one group on each agent alone and one group treated with the combination agents. A total of 10 evaluable patients per group will be necessary for study endpoints. To attain 10 patients in each arm who are evaluable for the primary endpoint, a total of 45 patients will be accrued to the study. Sample sizes of 10 per group allow for the estimation of the proportion of responders in evaluable patients to be within 31% of its true value with 95% confidence. Mean change will be compared between arms. Using standard deviations of change, a sample size of 10 per group will allow the detection of differences of 1.25 standard deviations between groups with 80% power assuming a two-tailed test and a Type I error rate of 5%.

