## **3.0 PATIENT ELIGIBILITY**

The target population for this study is patients with recurrent glioblastoma. This will be a single-center trial conducted at neuro-oncology clinic of Northwestern University.

A total of 30 evaluable subjects will be needed for this trial. The accrual cap is 45 patients, in order to cover those patients that do not make it to the first evaluable time point. Hence, the total accrual per arm will be up to 15. Approximately 4 potentially eligible patients are seen per month, and it is anticipated that at least 2 per month will be accrued. Potential patients may be referred to the Principal Investigator (PI) at Northwestern University, [name], at [contact].

Eligibility will be evaluated by the study team according to the following criteria. Eligibility waivers are not permitted. Subjects must meet all of the inclusion and none of the exclusion criteria to be registered to the study. Study treatment may not begin until a subject is registered.

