#### 4.6 Duration of Follow Up

All subjects will be followed for survival for up to 2 years/24 months from stopping study treatment. Subjects who decline to return to the site for evaluations will be offered follow-up by phone every 8-16 weeks as an alternative.

Note that patients who discontinue treatment permanently for any reason other than progression will be followed for evidence of tumor response and disease status.

Any patient who withdraws their consent, will be considered as an early discontinuation, and may be replaced if this occurs before they have received the first dose of treatment. Patients who withdraw consent but receive at least one dose of treatment will be evaluable for toxicity even if they are not fully evaluable for response. The accrual goal has been set to allow up to 45 patients to be enrolled in order to allow for early discontinuations.

If a patient withdraws consent, no further treatment or study-specific testing will be completed. The primary reason for a patient's withdrawal from the study is to be recorded in the source documents. All patients will be followed until death or 2 years/24 months from stopping treatment.

Subjects who are permanently discontinued from further receipt of investigational product, regardless of the reason (withdrawal of consent, due to an AE, other), will be identified as having permanently discontinued treatment.

Subjects who are permanently discontinued from receiving investigational product will be followed for safety for 30 days post last-dose visit including the collection of any protocol-specified blood specimens, unless consent is withdrawn or the subject is lost to follow-up or enrolled in another clinical study. If a subject is enrolled in another clinical study, they will be followed until all AEs are resolved or stable. If enrolled onto another clinical study, it is not necessary to follow the subject for survival or progression.

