#### 10.3 Sample Size, Accrual and Data Analyses Plans

There will be three groups of patients, one group on each agent alone and one group treated with the combination agent. There will be 10 patients per group for a total of 30 patients. These 30 patients must be evaluable for the primary endpoint, meaning that they must have undergone surgery and their blood and tissue samples are available at both the pre- and post-surgery times. In order to attain 10 evaluable patients in each arm, a total of 45 patients will be accrued to the study. Sample sizes of 10 per group allow for the estimation of the proportion of responders in evaluable patients to be within 31% of its true value with 95% confidence. Mean change will be compared between arms. Using standard deviations of change, a sample size of 10 per group will allow the detection of differences of 1.25 standard deviations between groups with 80% power assuming a two-tailed test and a Type I error rate of 5%.

Immunologic measures will be summarized over the three or more time points (pre-treatment, following first treatment/pre-surgery, post-surgery) and changes in these measures will be assessed using repeated measures analysis of variance or Cochran's Q, followed by the paired t-test or the signed rank test for pairwise comparisons using Bonferroni corrections. Safety of the agents alone or in combination will be assessed by summarizing the frequency of adverse events by type, timing, grade and attribution. Response criteria will be based on RANO (including upcoming Immunologic RANO criteria) but since all patients will be post-surgery, the degree, if any, of

residual disease will vary. A patient is evaluable for efficacy if they have undergone at least one follow-up MRI after adjuvant therapy. Immunologic changes will be correlated with MRIs in a descriptive fashion. The secondary endpoint of progression-free survival as well as overall survival will be analyzed using Kaplan-Meier curves. Immunologic changes of T-cells and PDL1 levels will be correlated to survival outcomes using Cox regression analysis. MRI changes will be summarized using means or proportions and statistically analyzed using the signed rank test.

**Performance Status:** Patients will be graded according to Karnofsky Performance Status (KPS)(see appendix C).

**Evaluation of toxicity.** All patients will be evaluable for toxicity from the time of their first treatment as per NCI CTCAE version 4.03

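### Section 4.2 still limits enrolment to 12 patients per arm, in conflict with the 15 per arm (45 in total) given elsewhere for the same target of 10 evaluable per arm

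*Combined protocol and SAP*

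**What the plan says.** Section 4.2 (Treatment Administration), in the paragraph below the treatment table, allocates patients by block randomisation "with up to 12 patients being enrolled into each arm (in order to achieve 10 evaluable per arm".

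The other current statements of accrual are:

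- **Section 4.1 (Overview):** "Up to 45 patients (15 per arm) will be randomized to ensure that 30 patients are evaluable for immunologic response (10 per arm".
- **Section 3.0 (Patient Eligibility):** "The accrual cap is 45 patients, in order to cover those patients that do not make it to the first evaluable time point", followed by "Hence, the total accrual per arm will be up to 15".
- **Section 4.6 (Duration of Follow Up):** "The accrual goal has been set to allow up to 45 patients to be enrolled in order to allow for early discontinuations".
- **Section 10.3 (Sample Size, Accrual and Data Analyses Plans):** "In order to attain 10 evaluable patients in each arm, a total of 45 patients will be accrued to the study".
- **Study Summary:** "To attain 10 patients in each arm who are evaluable for the primary endpoint, a total of 45 patients will be accrued to the study".

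Only Sections 3.0 and 4.1 print 15 per arm. Section 4.6, Section 10.3 and the Summary give the total of 45. Section 4.2 prints no total; 36 is 3 × 12.

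**The concern.** Both per-arm figures are written as upper limits, and both are justified by the same goal of 10 evaluable patients per arm. They cannot both be the limit. A 13th patient in an arm would comply with Sections 3.0 and 4.1 and exceed Section 4.2.

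The number sits in operative text on randomisation, and Section 11.6 requires the study to follow the approved protocol exactly, so the conflict is not purely cosmetic. If an arm were closed at 12, the primary comparison between arms could fall short of the 10 evaluable patients on which the stated power and precision rest. Being evaluable under Section 6.1 takes several steps: a pre-treatment blood sample, surgery with a pre-surgical sample, and continuation to post-operative treatment with a sample before the first post-surgical dose. Some loss is therefore to be expected.

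**Working it through.** **Inputs from the documents.** 10 evaluable per arm and 30 in total; accrual of 45 (15 per arm) or, in Section 4.2, 12 per arm; detectable difference 1.25 SD, 80% power, two-sided 5% test; half-width of 31% for a proportion (Section 10.3).

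**Assumption.** No attrition rate is stated. I use two yields: two-thirds, the lowest average yield at which 45 accrued still gives 30, and 80% as an alternative.

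**Step 1: reproduce the plan's own figures at 10 per arm.**
- Power, normal approximation: Φ(1.25 × √(10/2) − 1.96) = Φ(2.795 − 1.96) = Φ(0.835) = 0.798. This reproduces the stated 80%. A t-test calculation gives 0.753.
- Half-width: 1.96 × √(0.25/10) = 0.310. This reproduces 31%.

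The evaluable sample size in Section 10.3 therefore stands on its own terms, and the figure of 12 enters none of it.

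**Step 2: what each cap can absorb.**
- 15 per arm: 10/15 = 66.7% yield, so an average loss of up to one-third.
- 12 per arm: 10/12 = 83.3% yield, so an average loss of up to one-sixth (16.7%).

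**Step 3: expected evaluable patients at two-thirds yield.**
- 12 × 2/3 = 8 per arm (36 × 2/3 = 24 in total).
- 15 × 2/3 = 10 per arm (45 × 2/3 = 30 in total). This line is circular, because the yield was taken from 30/45. It shows consistency only.

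**Step 4: chance that one arm reaches 10 evaluable.** Binomial P(X ≥ 10), with patients independent. For 12 per arm at two-thirds: [66 × 2^10 + 12 × 2^11 + 2^12] / 3^12 = 96,256 / 531,441 = 0.181. The other values come from the same formula.

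| Yield | 12 per arm | 15 per arm |
|---|---|---|
| 66.7% | 0.18 | 0.62 |
| 80% | 0.56 | 0.94 |
| 83.3% | 0.68 | 0.97 |

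For all three arms together (cubing the unrounded values), the chances are 0.006 against 0.24 at two-thirds yield, and 0.17 against 0.83 at 80%.

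**Step 5: consequence if 8 per arm are evaluable.**
- Power: Φ(1.25 × √(8/2) − 1.96) = Φ(2.5 − 1.96) = Φ(0.54) = 0.705, down from 0.798. With the t-test it is 0.643, down from 0.753.
- Half-width: 1.96 × √(0.25/8) = 0.346, up from 0.310.

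**The case against.** The strongest reply is that nobody reading the whole protocol would be misled. Every other current statement of total accrual says 45, including the statistical section. Section 4.1, directly before Section 4.2, repeats the block randomisation statement with 15 per arm. The summary of changes records that Amendment 5 raised the cap from 36 (12 per arm) to 45 (15 per arm) with DSMC approval. This is a single-centre trial in which a QAM reviews and registers each patient, so closing an arm at 12 by mistake looks unlikely. This largely stands, and it leaves little doubt about which number was meant. It does not remove the conflict, which lies wholly between current sections.

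The probabilities also have limits. Even 15 per arm brings all three arms to 10 evaluable only 24% of the time at two-thirds yield, so the correction does not guarantee the target. The calculation treats enrolment per arm as fixed, whereas Section 4.8 replaces undosed patients and allows additions after discontinuation before surgery; the documents do not say whether these count against the per-arm limit.

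A reader might go further than the documents allow in three ways:

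- *That 12 per arm cannot deliver 10 evaluable.* It can. The chance for one arm is 18% at two-thirds yield and 56% at 80%, and at 83.3% yield the expected number is exactly 10.
- *That the plan expects to lose one-third of patients.* It states no rate, and 45 is a ceiling in Sections 3.0 and 4.1. One-third is the most the ceiling tolerates on average.
- *That the sample-size calculation is faulty.* It does not use the 12, and its figures reproduce as shown in Step 1.

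**Conclusion.** Wrong as written. Section 4.2 contradicts Sections 3.0 and 4.1 on the per-arm limit, and the total it implies (36) contradicts the 45 given in five places. It is an incomplete update of one number.

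The contradiction needs no assumption. The size of its effect does: it matters only if an arm were actually stopped at 12, and it depends on an attrition rate that the plan does not give. Under the least favourable average yield that 45 can absorb, the shortfall would be about 2 evaluable patients per arm, with the losses in power and precision shown in Step 5. At an 80% yield the expected number is 9.6 (12 × 0.8), so the shortfall is small on average, though an arm would still miss 10 in 44% of cases (1 − 0.56). The practical risk is low because the surrounding sections point clearly to 15. It remains worth correcting because the figure governs enrolment and randomisation.

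**What to change.** In Section 4.2, change the per-arm enrolment limit from 12 to 15, so that it matches Sections 3.0 and 4.1 and the total of 45 in Section 4.6, Section 10.3 and the Study Summary. The cost is one number in the protocol text. The higher cap is already recorded as DSMC-approved, and neither the analysis nor the evaluable sample size changes.

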# 4.3 Supportive Care Guidelines & Concomitant Medications/Restrictions on Study

#### 4.3.1 Supportive Care

All medications used by patients during the study, with the reasons for use, will be recorded in the medical record and documented in the appropriate eCRF. For all subsequent visits, all concomitant therapy that is continuing or has been added, discontinued, or had a dosage change since the previous visit must be recorded in the medical record/eCRF as well.

• Antiemetic therapy may be used as needed and will be recorded in the medical record; 5HT antagonists are recommended.

- Hematopoietic growth factors (G-CSF) may be used per American Society of Clinical Oncology (ASCO) guidelines after cycle one.
- Corticosteroids should be used in the smallest dose to control symptoms of cerebral edema and mass effect, and should be discontinued if possible. Please confirm appropriate use with the PI.
- Febrile neutropenia may be managed according to the institution's infectious disease/ASCO guidelines. Measures may include appropriate laboratory testing, including blood and urine cultures and the initiation of broad-spectrum antibiotics. If a source for the fever is not identified or the fever resolves when the neutrophil count recovers, antibiotics may be discontinued and the patient observed. In this case growth factors may be used.
- If neurosurgical intervention is required for indications not related to tumor progression, these procedures must be documented, including the indications for surgery, surgical operative note, and pathology report.

## 4.3.2 Restrictions While on Treatment

**Contraception** 

Females of childbearing potential who are sexually active with a nonsterilised male partner must use 2 methods of effective contraception (refer to appendices) from screening, and must agree to continue using such precautions for 90 days after the final dose of investigational product, or for at least 90 days following the last infusion of MEDI4736 or until after 4-5X the half-life of Tremelimumab, whichever occurs longest; cessation of birth control after this point should be discussed with a responsible physician. Periodic abstinence, the rhythm method, and the withdrawal method are not acceptable methods of birth control.

Females of childbearing potential are defined as those who are not surgically sterile (i.e., bilateral tubal ligation, bilateral oophorectomy, or complete hysterectomy) or postmenopausal (defined as 12 months with no menses without an alternative medical cause).

Non-sterilised males who are sexually active with a female partner of childbearing potential must use 2 acceptable methods of effective contraception (see appendices) from Day 1 and for 90 days after receipt of the final dose of investigational product.

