#### IRB #: STU00202283-MOD0025 Approved by NU IRB for use on or after 2/8/2019 through 1/6/2020. (Cockcroft and Gault 1976) or by 24-hour urine collection for determination of

creatinine clearance:

Males: Creatinine CL (mL/min)	$\frac{\text{Weight (kg) x (140 - Age) x 1.0}}{72 \text{ x serum creatinine (mg/dL)}}$
Females: Creatinine CL (mL/min)	$\frac{\text{Weight (kg) x (140 - Age) x 0.85}}{72 \text{ x serum creatinine (mg/dL)}}$

3.1.11 Females of child-bearing potential (FOCBP) and males must agree to use adequate contraception (e.g. hormonal or barrier method of birth control – see appendices acceptable birth control methods) prior to registration, for the duration of study participation, and for 180 days after the last dose of MEDI4736 + tremelimumab combination therapy or 90 days after the last dose of MEDI4736 or tremelimumab monotherapy. Should a female patient become pregnant or suspect she is pregnant while participating in this study, she should inform her treating physician immediately.

*NOTE:* A FOCBP is *any woman* (regardless of sexual orientation, having undergone a tubal ligation, or remaining celibate by choice) who meets both of the following criteria:

- *Has not* undergone a hysterectomy or bilateral oophorectomy.
- *Has had* menses at any time in the preceding 12 consecutive months (and therefore has not been naturally postmenopausal for > 12 months).
- 3.1.12 FOCBP must have a negative pregnancy test (serum or urine) within 7 days prior to registration on study.
- 3.1.13 Patients must have the ability to understand and the willingness to sign a written informed consent prior to registration on study.
- 3.1.14 Subject is willing and able to comply with the protocol for the duration of the study including undergoing treatment and scheduled visits and examinations including follow up.
- 3.1.15 Patients must have given written, signed and dated informed consent prior to registration on the study. NOTE: no study-specific screening procedures may be performed until consent has been given.

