### 7.2.7 Pregnancy

Pregnancy itself, or pregnancy of a subject's partner, is not regarded as an adverse event unless there is a suspicion that the investigational product under study may have interfered with the effectiveness of a contraceptive medication. Congenital abnormalities/birth defects and spontaneous miscarriages should be reported and handled as SAEs. Elective abortions without complications should not be handled as AEs. The outcome of any conception occurring from the date of the first dose until 90 days after the last dose (spontaneous miscarriage, elective termination, ectopic pregnancy, normal birth or congenital abnormality) should be followed up and documented even if the subject was withdrawn from the study.

Pregnancy in a female subject who has received investigational product is required to be reported *within 24 hours of knowledge of the event* to the QAM and AstraZeneca/MedImmune Patient Safety or designee using the designated Safety e-mailbox (7.3.3.4).

Subjects who become pregnant during the study period must not receive additional doses of investigational product but will not be withdrawn from the study. The pregnancy will be followed for outcome of the mother and child (including any premature terminations) and should be reported to AstraZeneca/MedImmune Patient Safety or designee after outcome. Male subjects should refrain from fathering a child or donating sperm during the study and for through 180 days after the last dose of MEDI4736 + tremelimumab combination therapy or 90 days after the last dose of MEDI4736 or tremelimumab monotherapy.

Should the investigator become aware of a pregnancy in the partner of a male study subject who has received investigational product this should be reported *within 24 hours of knowledge of the event* to the QAM and AstraZeneca/MedImmune Patient Safety or designee using the Safety Fax Notification Form. The funding sponsor will endeavor to collect follow-up information on such pregnancies provided the partner of the study subject provides consent.

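### For Arm 3, section 4.3.2 states a shorter post-treatment contraception period than the 180 days in 3.1.11 and 7.2.7, and it counts tubal ligation as sterility where 3.1.11 does not

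*Combined protocol and SAP*

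**What the plan says.** Three sections of the protocol deal with contraception after the last dose.

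- **3.1.11 (inclusion criteria)** applies to females of childbearing potential and to males. Both must agree to contraception "for 180 days after the last dose of MEDI4736 + tremelimumab combination therapy", or for 90 days after either drug given alone.
- **4.3.2 (restrictions while on treatment)** makes no distinction by arm. A woman "must agree to continue using such precautions for 90 days after the final dose of investigational product", or for a minimum of 90 days from the last MEDI4736 infusion, or "until after 4-5X the half-life of Tremelimumab, whichever occurs longest". It adds that "cessation of birth control after this point should be discussed with a responsible physician". Men must use contraception "from Day 1 and for 90 days after receipt of the final dose of investigational product".
- **7.2.7 (pregnancy)** separates the combination from monotherapy as 3.1.11 does: "Male subjects should refrain from fathering a child or donating sperm during the study and for through 180 days after the last dose" of the combination, and 90 days after monotherapy.

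Two sections define childbearing potential. Section 4.3.2 lists bilateral tubal ligation among the forms of surgical sterility. The note to 3.1.11 says that tubal ligation makes no difference: a woman counts if she has had neither a hysterectomy nor a bilateral oophorectomy and has menstruated within the past 12 months.

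**The concern.** Section 4.3.2 is the only part of the treatment plan (section 4) that sets a contraception period. A patient gives the 3.1.11 agreement before registration, but the period after the last dose may begin as much as 24 months later. Staff advising an Arm 3 patient at that point could reasonably turn to section 4. If they applied 4.3.2 as written, they would release the patient earlier than 3.1.11 allows and, for a man, earlier than 7.2.7 allows. Women at least have a physician discussion built into 4.3.2; men do not. Section 11.6 calls for strict adherence to the protocol, yet the protocol gives two periods for the same patient.

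The two definitions add a second conflict. A woman with a tubal ligation who still menstruates must use contraception under 3.1.11 and is exempt under 4.3.2.

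**Working it through.** **Inputs.** 180 days after combination therapy (3.1.11, both sexes; 7.2.7, men). 90 days, or 4 to 5 tremelimumab half-lives if longer, for women, and 90 days for men (4.3.2). Tremelimumab terminal half-life 22.1 days (1.4.1). From Cycle 7 in Arm 3, tremelimumab every 12 weeks and MEDI4736 every 2 weeks (5.2, footnote 14).

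**Women, last doses on the same day.** Period under 4.3.2 = max(90, k × 22.1).

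- k = 4: 4 × 22.1 = 88.4, so the 90-day floor governs and the period is 90 days.
- k = 5: 5 × 22.1 = 110.5 days.

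Section 4.3.2 states neither 88.4 nor 110.5; both follow from applying the half-life in 1.4.1.

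**Women, last tremelimumab dose g days before the last MEDI4736 dose.** Section 4.3.2 does not say when the half-life clause starts. Assume it runs from the last tremelimumab dose. Counted from the last MEDI4736 dose, the period with k = 5 is then max(90, 110.5 − g).

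- g = 14: 110.5 − 14 = 96.5 days.
- g = 28: 110.5 − 28 = 82.5, so 90 days.
- Any g of 20.5 days or more (110.5 − 90) gives 90 days. This can happen from Cycle 7, when tremelimumab doses are 84 days apart.

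**Shortfall against 180 days in Arm 3.**

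| | 4.3.2 | 3.1.11 | Difference |
|---|---|---|---|
| Men | 90 d | 180 d | 90 d (90/180 = 50%) |
| Women, longest reading | 110.5 d | 180 d | 69.5 d (69.5/180 = 39%) |
| Women, shortest reading | 90 d | 180 d | 90 d (50%) |

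The 4.3.2 rule does not give 180 days with 4 or with 5 half-lives, whether the last doses coincide or are staggered.

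**Monotherapy.** In Arms 1 and 2, 4.3.2 gives men 90 days and women at least 90 days, against 90 days in 3.1.11. It is not shorter there.

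**Definitions side by side.**

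| Woman | 3.1.11 | 4.3.2 |
|---|---|---|
| Tubal ligation, still menstruating | childbearing potential | exempt |
| No menses for 12 months, from a medical cause | read literally, exempt | childbearing potential |

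The second row arises because 4.3.2 accepts 12 months without menses as menopause only when no other medical cause explains it. The menses criterion in 3.1.11 has no such proviso, although its mention of natural menopause leaves some doubt. Neither definition is the stricter one throughout.

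**The case against.** The strongest reply is that the periods are compatible. A patient who uses contraception for 180 days meets the duration in every section. The 3.1.11 agreement covers the time after treatment and is not cancelled by 4.3.2, and eligibility waivers are not allowed. Section 7.2.7 gives Arm 3 men the 180-day limit directly. For women, 4.3.2 sets minimum periods and then asks for a discussion with a physician. All of this stands and lowers the weight of the point. It does not make the 4.3.2 text right for Arm 3, because it relies on the reader finding and applying the stricter section.

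A reader might infer more than the documents support:

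- **That the protocol as a whole requires only 90 days of Arm 3 patients.** It does not; 3.1.11 and 7.2.7 remain in force. The percentages compare sections and do not measure a gap in the whole protocol.
- **That pregnancies after day 90 would go unfollowed**, because one sentence in 7.2.7 limits follow-up of conception outcomes to 90 days after the last dose. For a participant who becomes pregnant in the study period, 7.2.7 also says: "The pregnancy will be followed for outcome of the mother and child". For partners of male participants, the funding sponsor "will endeavor to collect follow-up information on such pregnancies", subject to the partner's consent and with no day limit.
- **That women with a tubal ligation escape the entry pregnancy test.** They do not; 3.1.12 uses the term as 3.1.11 defines it.
- **That harm to a fetus is shown.** Section 1.4.1 reports no developmental toxicity or teratogenicity for tremelimumab in monkeys. That study does not address MEDI4736 or the combination, so it neither shows harm nor justifies the shorter period.

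**Conclusion.** The inconsistency is in the current text. For Arm 3, 4.3.2 is 90 days short of 180 for men and 69.5 to 90 days short for women. The women's range rests on the 22.1-day half-life, and its favourable end also requires the last doses of the two drugs to coincide. Two sections treat the combination separately and one does not, so the protocol itself shows that 4.3.2 is the one out of line.

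The reach is small. Arm 3 is capped at 15 patients, and only women of childbearing potential and men with such partners are affected; the documents do not give their number. The consent pages are not in the documents reviewed, so what patients are told there cannot be checked. Sample size, power, type I error and the endpoints are untouched. The point is worth correcting because it concerns a safety instruction and the remedy is simple.

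**What to change.** In 4.3.2:

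1. State 180 days after the last dose of combination therapy for both sexes in Arm 3. Leave the monotherapy periods as they are.
2. Delete bilateral tubal ligation from the list of surgical sterility. Keep the proviso that 12 months without menses counts as menopause only when there is no other medical cause.

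Do not replace the whole 4.3.2 definition with that of 3.1.11. That would bring in women with a tubal ligation but could exempt women whose amenorrhoea has a medical cause.

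The cost is a wording amendment to one section, with no added visits, tests or analyses. Affected Arm 3 patients would see 4.3.2 lengthen by 90 days (men) or 69.5 to 90 days (women), to the period they already agree to under 3.1.11. Women with a tubal ligation would come under the 4.3.2 contraception rule, as they already do under 3.1.11.
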